**Table 2. Estimated retention at each perinatal period**

	2 nd Trimester (18-24 weeks)	3 rd Trimester (30-36 weeks)	Postpartum (1-2 months)	Postpartum (5-6 months)
Usual Care	50	45	39	28
B-EPIC	50	45	39	28
Total	100	90	78	56

**Inclusion criteria:** 1) current diagnosis of opioid dependence with participation in the buprenorphine treatment program; 2) less than 32 weeks gestation; 3) age 18-49 years old; 4) diagnosis of current tobacco use disorder; and 5) read or write in English. **Exclusion criteria:** Women are excluded if they have current prisoner status, current severe mental illness (e.g., bipolar disorder with current mania, current suicidal ideation), or alcohol or sedative/hypnotic dependence that requires medical intervention.

**Recruitment, Screening and Informed Consent:** Institutional Review Board (IRB) approval will be obtained from the University of Kentucky for this study. The screening, recruitment and retention plan is anchored by our previous work among pregnant and postpartum women who smoke. All study personnel will have completed human subjects training - and good clinical practice (GCP) research training. There will be two methods of recruitment: 1) study flyers will be posted in highly visible areas in the UKHC MAT clinics for pregnant/postpartum women and 2) the research nurse will provide an overview of the B-EPIC study in the buprenorphine treatment clinic for pregnant women. At conclusion of the overview, all women will be given a flyer in which they can either check that they are interested in screening for the study, verbally let the research nurse know they are interested in screening, and also be given the study recruitment phone number. Volunteers interested in the study will be screened for eligibility by research staff and those meeting initial eligibility screening criteria will be invited to come in for an in-person screening whereby informed consent will be completed before any study procedures are initiated (see Human Subjects).

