**Randomization:** After informed consent and screening are completed, participants meeting study inclusion/exclusion criteria will be randomized (1:1) to the B-EPIC group (tobacco intervention) or TAU tobacco treatment (control group). All will continue to receive opioid dependence treatment with buprenorphine, regardless of treatment assignment. Randomization will be stratified by age (30+ vs less than 30). We will create a separate randomization schedule for each age stratum using the PLAN procedure in SAS (SAS Institute, Inc.); each schedule will include 17 blocks of 6 participants, with half per block randomized to each of the two treatment groups. Recruitment in this fashion will ensure an approximately equal number of subjects in each group throughout the enrollment period in both age strata, and we will continue recruitment until we have enrolled 100 subjects.

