**Study Procedures.** Participants will be asked to provide urine samples and complete a survey at four times throughout the study (2nd and 3rd trimester, and 1-2 months, 5-6 months after delivery). There will be minimum of 8 weeks between individual data collection time periods. First, a survey available via iPad (paper/pen by request) will be administered by the research staff. The survey will take approximately 20 minutes to complete and will assess current and past use of tobacco products, demographic and psychosocial variables, stage of change, and personal characteristics; skip patterns will be used if indicated to minimize respondent burden. See Table 4. The survey will be stored on RedCap, a secure web-based data management system managed through the UK Clinical and Translational Research Center. The research nurse will then collect prenatal biomarkers (urine for cotinine and drug testing). [name] (PI) will train all study personnel collecting prenatal biomarkers consistent with procedures refined in previous studies. Participants will be informed their urine will be tested for cotinine (metabolite of nicotine) and other illicit drugs to confirm tobacco and/or illicit substance use at each data collection point and informed of their results in compliance with American Congress of Obstetricians and Gynecologists (ACOG) clinical standards. Participants will be informed their survey and biomarkers results will remain confidential. Confidentiality will be maintained through the use of non-identifying subject numbers; all study data will be saved daily on a secure server in a password-protected folder.

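### Fixed blocks of 6, with no allocation concealment described, would let a staff member who tracked assignments foresee up to a quarter of them

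*Combined protocol and SAP*

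**What the plan says.** The Randomization paragraph sets a 1:1 allocation after consent and screening. "Randomization will be stratified by age (30+ vs less than 30" versus younger defines two strata, each with its own list from the SAS PLAN procedure, and "each schedule will include 17 blocks of 6 participants, with half per block randomized to each of the two treatment groups". Enrolment is open-ended within strata: "we will continue recruitment until we have enrolled 100 subjects".

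Under Recruitment, Screening and Informed Consent, "the research nurse will provide an overview of the B-EPIC study in the buprenorphine treatment clinic for pregnant women", and "Volunteers interested in the study will be screened for eligibility by research staff". Under Study Procedures, research staff administer the surveys at the four assessments, and "The research nurse will then collect prenatal biomarkers (urine for cotinine and drug testing").

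The B-EPIC Intervention paragraph adds specialist tobacco sessions (a 60-minute first assessment, then sessions of 15-20 minutes), biomarker feedback and pharmacotherapy as needed to usual care. The CTTS Training paragraph says that the specialist is a nurse already working at the site.

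Nothing in the document describes varying block sizes, who holds the lists, how an assignment is released, or blinding of any role. The section on potential risks limits access to data and identifiers and mentions breaking the study code. That concerns confidentiality and does not describe concealment of the next allocation.

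**The concern.** In a block with three places per arm, the remaining places are fixed as soon as one arm has its three. Anyone who knows the block size and the assignments so far in that stratum then knows the next arm before a woman is consented. The conditions for such knowledge are not excluded here: the size is constant and stated in the protocol, there are only two strata, the arms differ in ways that clinic staff can see, and the roles that bring women in also see them after randomization.

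The stake is selection bias. A staff member who foresees the next arm could, even without intent, hasten or delay the screening of a woman who seems keen to quit. Cigarettes per day and stage of change are among the several primary outcomes, and both plausibly depend on motivation at entry. The Power Considerations section says that the effect sizes are meant to plan larger studies, so any distortion would carry forward.

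**Working it through.** The plan states no figure for predictability. The one figure to reproduce is the list length: 100/6 = 16.7, rounded up to 17 blocks, and 17 × 6 = 102 places. Either list could therefore hold all 100 women whatever the age split, which agrees with the plan.

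**Inputs.** Block of 6, 3 per arm, two strata, 100 women (Randomization paragraph). Assumption for the upper limit: the observer knows the block size, where each block starts, and every previous assignment in the stratum.

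**Step 1: certain allocations in a complete block.** There are C(6,3) = 20 equally likely orders. An allocation is certain when one arm already has its three.

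| Place in block | 1 | 2 | 3 | 4 | 5 | 6 |
|---|---|---|---|---|---|---|
| Chance that it is certain | 0 | 0 | 0 | 0.10 | 0.40 | 1.00 |
| Best guess correct | 0.50 | 0.60 | 0.60 | 0.70 | 0.70 | 1.00 |

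The first row sums to 1.5, and 1.5/6 = 25%. The closed form with m places per arm, 2m/(m+1), gives 6/4 = 1.5 for m = 3. The second row, guessing the arm with fewer so far, sums to 4.1, and 4.1/6 = 68.3%, against 50% by chance.

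**Step 2: the whole trial.** The last block in a stratum may be unfinished. For 50 women in a stratum there are 8 full blocks and 2 further places: 8 × 1.5 + 0 + 0 = 12.0, so 24.0 over two such strata. Over every possible age split the expected number lies between 23.5 and 24.1 of 100.

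**Step 3: incomplete knowledge.** Suppose that each previous assignment is known independently with probability q (an assumption; the documents give nothing on this). Certainty requires knowing the three assignments that filled one arm, so the share is 25% × q³.

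| q | Certain allocations |
|---|---|
| 1.0 | 25% |
| 0.9 | 18% |
| 0.8 | 13% |
| 0.7 | 9% |

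**Step 4: varying block sizes.** This was a simulation of 2,000 runs of a 50-woman stratum. The observer knows the possible sizes but not their order, and updates by Bayes' rule after each assignment.

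| Block sizes | Certain | Best guess correct |
|---|---|---|
| 6 only | 23.9% | 67.8% |
| 4 or 6 | 5.7% | 69.0% |
| 4, 6 or 8 | 2.3% | 67.7% |

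The simulated 23.9% for fixed blocks agrees with the exact 24.0% from Step 2. Varying the size removes most of the certainty and almost none of the ability to guess.

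**The case against.** The case for leaving the design alone has real substance.

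- A reader might infer that a quarter of allocations were in fact known to recruiters. The documents do not support that. No section says that recruiting staff know the block size, see the list or keep a tally by stratum. The research nurse's stated tasks are the same in both arms, and a separate specialist leads the intervention. This stands, and it is why the figure is an upper limit. It does not remove the point, because nothing in the plan keeps this knowledge from those staff.
- Recruiters have limited discretion. Flyers are posted openly and given to all women at the overview, and women volunteer themselves. Randomization already follows consent and screening. This weakens the idea of selective approach, but the timing of screening is still open to influence.
- A reader might infer that any bias would be beyond repair. That is too strong. Readiness to quit, nicotine dependence and cigarettes per day are listed under Covariates, and the Statistical Analysis Plan adjusts for factors that differ between groups. The repair is partial: by the plan's own figure, the baseline comparison has 84% power only for a difference of 0.6 standard deviations, and adjustment cannot reach unmeasured motivation.
- A reader might also infer that motivation governs the main outcome. The plan has several primary outcomes, including gestational age, birthweight and neonatal abstinence syndrome. Its Power Considerations section cites a study in which readiness rose without a higher quit rate.
- Varying block sizes barely changes best-guess accuracy. This stands, so the change must be paired with concealment of the list and the sizes.
- Fixed permuted blocks are a recognised choice, and this is an exploratory pilot. That bears on how much weight the point carries, not on whether it is correct.

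**Conclusion.** The concern holds as a statement about what the design permits. With fixed blocks of 6 and no concealment described, a fully informed staff member could be certain of 25% of allocations per complete block, about 24 of 100 women. The share falls to between 9% and 18% if each previous assignment is known with probability 0.7 to 0.9.

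Two elements are inferred. The trial is taken as unblinded because the intervention is mainly behavioural and visible and no blinding is described. Staff knowledge of previous assignments is taken as possible because the same roles recruit or screen women and follow them up. Concealment may exist in practice without being written down. There is no evidence that selection occurred, and the size of any resulting bias cannot be calculated from the documents. This is a worthwhile, low-cost improvement and not a flaw that undermines the trial.

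**What to change.** Three changes to the Randomization paragraph:

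1. Generate each age-stratum list in the PLAN procedure with block sizes drawn at random, for example from 4, 6 and 8, and make each list at least 100 places long.
2. State who holds the lists, and keep both the lists and the block sizes from recruiting and screening staff, including in documents that the clinic sees.
3. State that each assignment is revealed only after the consent and eligibility that the plan already requires have been recorded. REDCap, already used for the survey, could hold that record.

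The cost is a few lines of code and a short protocol edit. Sample size, stratification, 1:1 ratio and analysis are unchanged. The downside is balance. An unfinished block of 6 can leave one arm ahead by at most 3 in a stratum (6 over both strata), and an unfinished block of 8 by at most 4 (8 over both).

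If enrolment is already complete, report how allocation was in fact concealed, and use varying blocks in the larger study that this pilot is meant to inform.

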**Follow up data collection:** Healthcare outcome data will be collected from the mother's and infant's electronic medical record and national MEPS data. Maternal data obtained includes: prenatal history, medications and complications, gestational age at birth, birthweight, delivery method and complications, hospital readmissions, medical care adherence/attendance, readmission, emergency room visits and number of positive urine drug testing results. Infant data obtained from the maternal medical record or national MEPS data includes: sex and birth weight, NICU admission, length of NICU stay, NAS scores, treatment offered for NAS/total mg dose in morphine equivalents of such treatment, infant outpatient visits, including, well-child, sick visits and emergency department. Our team has successfully established methods to increase retention through the perinatal period by encouraging open and engaging communication. Various communication methods include: regularly scheduled (monthly) contact, telephone calls, post cards, emails, and text messaging. Preferred methods of communication will be used (as indicated by the participant).

**Compensation:** Participants are compensated for study completion in the form of gift cards (\$20-\$40 value). Gift cards are given in-person at prenatal and postpartum appointments. To bolster retention in the postpartum period we have increased the gift card value from \$20 to \$40. Participants will receive an additional \$20 gift card if three of four data collection points are completed. Refer to Table 3.

**Usual Care (TAU):** Women enrolled in the control group are informed of the risks of tobacco use and benefits of quitting using the ACOG 5'A's approach (see Box 1) by their healthcare provider. This standard takes approximately 5-15 minutes, and is offered at each prenatal and postpartum appointment.

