**Handling Missing Data.** Based on our prior longitudinal studies with pregnant and postpartum women, we anticipate retention to be at least 60% (9-12% attrition from 2nd-3rd trimester through 1-2 months postpartum; additional 30% attrition to 5-6 month postpartum), as shown in Table 2. The power estimates outlined below are expected to be conservative for several reasons: 1) attrition in the current UKHC MAT program is 12%; 2) we will use escalating and completion incentives to encourage completion; and 3) increased options for follow-up communication (email, text), using each participant's preferred communication method. Maternal and infant outcome data will be extracted from the UKHC medical record and national MEPS, reducing participant burden. Nonetheless, missing data will occur in this vulnerable population and we acknowledge this in the analysis, given that our analysis strategies allow for inclusion of participants who are missing one or more assessments. We will use the intention to treat convention (those randomized to the B-EPIC group will be retained in this group in the analysis whether or not they complete the entirety of the intervention). For the tobacco use indicators, we will examine group differences assuming the last observation carried forward (LOCF; e.g., if a participant is an active smoker at one time-point, we will assume this status at future time-point(s), if she drops out). We will conduct initial analyses using the maximum likelihood approach, as it emphasizes the use of all available data. The use of random effects modeling techniques, including repeated measures mixed modeling, allows for missing data by adjusting the estimation process to account for bias resulting from data missing at random. In addition, multiple imputation will be used as an alternative procedure for handling missing data. Multiple imputation produces results similar to maximum likelihood when used under identical conditions. The strategy of observing differences in group comparisons under these two methods of dealing with missing data is suggested by Hedeker et al. as a way to determine the robustness of the results under these different assumptions. This approach will provide a sensitivity analysis of the group comparisons.

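### The protocol describes no remote fallback for the survey when a reachable woman misses a visit, although Table 2 expects 44 of 100 lost by 5-6 months postpartum

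*Combined protocol and SAP*

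**What the plan says.** In the protocol's Study Procedures, each of the four assessments starts with a survey: "a survey available via iPad (paper/pen by request) will be administered by the research staff". The research nurse then collects urine for cotinine and drug testing, so the contact described is face to face. The survey data sit on a platform that could be used remotely: "The survey will be stored on RedCap, a secure web-based data management system".

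Under Compensation, "Gift cards are given in-person at prenatal and postpartum appointments". Under Follow up data collection, the retention effort consists of "regularly scheduled (monthly) contact, telephone calls, post cards, emails, and text messaging". These channels are listed for keeping in touch, not for collecting data. The reference to telephone and online delivery under CTTS Training concerns the counselling service.

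Table 2 ("Estimated retention at each perinatal period") gives 50, 45, 39 and 28 per arm. Handling Missing Data in the SAP expects retention of at least 60% and cites Table 2 for it. Power Considerations uses 30 completers per arm. The SAP names cigarettes per day and stage of change among the primary outcomes.

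**The concern.** As written, a woman who answers a text message but does not come in contributes neither urine nor self-report at that visit. The urine cannot be had without her. The self-report could be, on a platform and through channels that the study already has.

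The self-reports matter here. Power Considerations cites a prior study of similar size in which the quit rate did not improve but readiness did, and gives that as the reason for measuring stage of change. The plan relies on maximum likelihood, multiple imputation and last observation carried forward for missing values. The first two assume that data are missing at random, and the third assumes an unchanged status. An answer that was actually collected is better than any of these. What is at stake is the precision of the late postpartum comparison and its exposure to bias if women who stop attending smoke differently.

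**Working it through.** **Expected loss.** Table 2 gives 100 − 56 = 44 women lost, or 22 per arm. The stepwise attrition is 10/100 = 10.0%, 12/90 = 13.3% and 22/78 = 28.2%. Retention of at least 60% would mean at most 40 lost, or 20 per arm. The two figures disagree slightly.

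**The plan's own power figure.** For the group effect over m = 4 visits, the noncentrality is λ = f²·N·m / [1 + (m − 1)ρ], with 1 and N − 2 degrees of freedom. The plan gives f = 0.25 but not ρ. With ρ = 0.3 and N = 60, λ = 0.0625 × 60 × 4 / 1.9 = 7.89 and power is 78.9%, against 79% stated. With Table 2's N = 56, λ = 7.37 and power is 76.0%.

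**Simple single-visit precision.** The 95% half-width for a standardised difference is 1.96·√(2/n). The documents give no rate of remote response, so 25-50% of the 22 missing per arm is an assumption.
- n = 28: 0.524
- n = 28 + 5.5 = 33.5: 0.479 (9% narrower)
- n = 28 + 11 = 39: 0.444 (15% narrower)

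This ignores earlier visits, so it is not the planned analysis.

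**Precision under the planned mixed model (continuous outcomes).** Assume monotone dropout. Table 2 then gives, per arm, 5 women with visit 1 only, 6 with visits 1-2, 11 with visits 1-3 and 28 with all four. For each pattern p, V_p = (1 − ρ)I + ρJ over the visits observed. The information on an arm's four visit means is the sum of n_p·V_p⁻¹. The variance matrix of the arm differences is twice its inverse, and half-widths are 1.96 × the square root of the relevant variance. Remote response adds a visit-4 value for the same share of each incomplete pattern. The SAP specifies an exchangeable structure only for its GEE models; using it here, with ρ from 0.3 to 0.7, is an assumption.

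| ρ | 5-6 month half-width now | 25% respond | 50% respond | Visit-averaged effect narrows by (25%, 50%) |
|---|---|---|---|---|
| 0.3 | 0.506 | 0.467 (7.7%) | 0.437 (13.7%) | 1.8%, 3.1% |
| 0.5 | 0.482 | 0.451 (6.5%) | 0.427 (11.4%) | 1.2%, 2.1% |
| 0.7 | 0.451 | 0.430 (4.6%) | 0.415 (8.1%) | 0.7%, 1.2% |

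If the responders are all women lost after the 1-2 month visit, the ranges become about 4-13% and 0.4-2.4%.

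**Bias.** Suppose the arm difference among missing women departs by an assumed 0.5 SD from that in attenders. A completer comparison at 5-6 months is then biased by 0.44 × 0.5 = 0.22 SD. If responders are a random sample of the missing, this falls to 0.33 × 0.5 = 0.165 SD (25% respond) or 0.22 × 0.5 = 0.11 SD (50%). If they behave exactly like attenders, the observed difference does not move and the bias stays at 0.22 SD.

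**The case against.** The strongest case against is that this is an operational preference in an exploratory pilot that already has monthly contact, preferred channels, and escalating and completion incentives. The main cessation outcome is defined by cotinine and gains nothing. What is added is unverified self-report, in a trial where one arm receives biomarker feedback, so misreporting could differ by arm. With about 5-11 remote responders per arm, a sensitivity analysis by mode could not settle that. These points stand and limit the weight of the recommendation.

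A second objection concerns the full survey. Table 4 includes partner violence, childhood abuse and recent illicit drug use, and the protocol names loss of confidentiality as a risk. Sending all of it to an unsupervised and possibly shared phone would be unwise, and full payment without urine could weaken attendance. Both points stand and shape the fix.

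A reader might also infer more than the documents support:
- *That remote completion is ruled out.* It is not forbidden. In-person completion is inferred from the single mode described.
- *That a missed visit removes all self-reported outcomes.* Only that visit's answers are lost. Earlier answers stay in the mixed model, record-based outcomes are unaffected, and a missed appointment may be rebooked within its window.
- *That Aim 3 time-loss data go missing with the survey.* Table 4 has no time-loss item, and the Aim 3 Measures text names no instrument or mode for it. Utilization is also taken from medical records.
- *That 32 more women are still reachable (88 against 56).* The SAP says "attrition in the current UKHC MAT program is 12" per cent, without a period, and offers it as a reason why its estimates are conservative. Women still attending that clinic could be surveyed there and give urine.

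**Conclusion.** The gap is real, and closing it is a cheap improvement; it does not correct an error. No route is described for collecting self-reports from a woman who is reachable but absent, at a visit where the plan expects 40-44% to be missing. The benefit is confined to self-reported tobacco use, dependence, stage of change and readiness.

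Under the planned mixed model the gain is roughly 5-14% in the 5-6 month contrast and about 1-3% in the visit-averaged group effect. The 9-15% from the single-visit formula overstates it. The estimates rest on an assumed 25-50% response, spread evenly over the missing women, and on monotone dropout and exchangeable correlation of 0.3-0.7. They apply to continuous outcomes; stage of change analysed as categorical by GEE was not calculated. Bias may fall, but by how much depends on how closely remote responders resemble the other missing women, which the documents cannot show.

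**What to change.** **Study Procedures.** State that a woman who has not attended by a set point in the visit window is offered a short module by REDCap link or telephone. It should cover cigarettes and e-cigarettes per day, dependence, stage of change and readiness. Leave out the partner-violence, childhood-abuse and illicit-drug items. If staff already intend to use the telephone, say so.

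**Compensation.** Allow part of the visit's gift card to be sent electronically for a completed module, and keep the rest for the visit with urine. State whether a remote module counts towards the bonus for three of four time-points.

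**SAP.** Record the mode of completion and repeat the cigarettes-per-day and readiness analyses without remote responses. State that cotinine-defined abstinence still requires urine. Reconcile Table 2 (56 retained) with the text (at least 60%) and the power basis (30 per arm).

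**Cost.** A minor amendment with ethics review, a short REDCap form, and some time from existing staff. The remaining downsides are unverified self-report, differences between modes, and a possible small effect on attendance, which the split payment is meant to limit.
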